### 6.2. Analysis Populations

The following analysis populations are planned for this study:

- **Randomized Population:** All subjects who are randomized via the IWRS.
- **Full Analysis Set (FAS):** Subjects who are randomized, received at least one dose of

study drug and have a baseline and at least one valid post-baseline assessment of monthly migraine based on the headache diary data. The FAS will be used for all efficacy analyses with treatment classification based on the randomized treatment.

- **Per Protocol Analysis Set (PPS):** includes all subjects in the FAS who have completed Visits 1-8 with no missing MMDs and no important protocol deviations. The PPS will be used for supplementary analyses of the primary and secondary efficacy endpoints with treatment classification based on the treatment received.
- **Safety Analysis Set (SAF):** includes all subjects randomized into the study who received at least 1 dose of study medication. Data will be analyzed according to the treatment received. All safety analyses will be conducted using the Safety Population.

### **6.3. Interim Analysis and Data Monitoring**

[figure not shown]
No interim analyses are planned.

### **6.4. Adjustments for Covariates**

Where relevant, respective baseline values will be included in the statistical models as covariates.

### **6.5. Hypotheses**

The primary objective of this study is to test the null hypothesis ( $H_0$ ) that there is no difference in the mean change from baseline in the monthly (28-day) rate of migraine days (MMDs) during the last 4 weeks of the 20-week double-blind Treatment Phase relative to the Prospective Baseline Period between the SPN-538 and placebo groups.

## 6.7. Handling of Dropouts or Missing Data

### 6.7.2. Missing Safety Variables

Missing dates for AEs and non-study concomitant medications will be imputed as described in using the following rules:

If partial AE or medication dates occur, the convention for replacing missing dates for the purpose of statistical analysis is as follows.

For partial AE and medication start dates:

- If the year is unknown, then do not impute the date but assign a missing value.

- If the year is known, but the month or month and day is/are unknown, then:
  - If the year matches the year of first dose date and the end date (if present) is after first dose date, then impute as the month and day of the first dose date.
  - Otherwise, assign 01 January.
- If the year and month are known, but the day is unknown, then:
  - If the month and year match the month and year of the first dose date, then impute as the day of the first dose date.
  - Otherwise, assign 01.

For partial AE and medication end dates:

- If the year is unknown, then do not impute the date but assigned as missing value.
- If the year is known, but the month or month and day is/are unknown, then:
  - If the year matches the year of the last date of the study (date of last contact if subject lost to follow-up; date of completion or early termination), then impute as the month and day of the last date of the study.
  - Otherwise, assign 31 December.
- If the year and month are known, but the day is unknown, then:
  - If the month and year match the month and year of the last date of the study, then impute as the day of the last date of the study.
  - Otherwise, assign the last day of the month.

If partial times occur, the convention is as follows:

- if the missing time occurs on the day of the first dose and both the hour and minute are missing, then the time assigned is the time of the first dose, otherwise if both the hour and minute are missing and the date is not the date of first dose the time assigned is 12:00;
- if the date is the same as the date of the first dose and
  - only hour is missing, the hour assigned is 12 or the hour of first dose, whichever is later;
  - only the minute is missing, the minute assigned is 30 or the minute of first dose, whichever is later;
- Otherwise if the date is not the same as the date of first dose, the hour assigned is 12 if the hour is missing and the minute assigned is 30 if the minute is missing.

Missing data for all other safety endpoints will not be imputed

## **6.8. Analysis Visit Windows**

Data from scheduled visits will be analyzed. Visits will be analyzed as scheduled. Unscheduled measurements will be excluded from the descriptive statistics and statistical analyses of efficacy data but will be included in listings. Safety data from unscheduled visits may be included in summaries and listings as applicable.

## **6.9. Pooling of Sites**

This is a multicenter study. The primary analysis will be performed without site as a factor. Data from all sites will be pooled together for all analyses unless otherwise specified.

## 6.10. Study Subjects and Demographics

### 6.10.1. Disposition of Subjects and Withdrawals

Disposition will include tabulations of the number and percentage of subjects in each of the following categories by treatment group and overall:

- Subjects in the Randomized Population
- Subjects in the FAS
- Subjects in the PPS
- Subjects in the SAF

Within each of the previous categories, the number and percentage of subjects who completed, early discontinued and the reason for early discontinuation from the study will be summarized. The primary reason for early discontinuation may include any of the following:

- Withdrawal of consent and assent
- Lack of efficacy
- Investigator decision
- Noncompliance with study procedures
- Occurrence of unmanageable AEs
- Lost to follow-up
- Other

Subject disposition for screened subjects will be summarized. Subject enrollment distribution by site will be summarized using number and percent of subjects by each site.

Listing of screen failures among screened subjects will be presented for all screened subjects. Subject visit status at each visit and visit dates will be presented for randomized subjects.

### 6.10.2. Demographics and Other Baseline Characteristics

Demographic/baseline variables including age, sex, ethnicity, race, BMI, age group (6-8 vs. 9-11 years), race group (White vs non-white), Retrospective 3-months headache history score, PedMIDAS score, height and weight at screening will be summarized for the ITT population descriptive statistics for continuous variables and using counts and percentages for categorical variables and listed.

Baseline comparability among the treatment groups will be summarized using a chi-squared test for the categorical variables and using a t-test for the continuous variables. These p-values will be used for descriptive purposes and will not be considered as the formal basis for determining factors to be included in statistical analysis model.

Medical history will be coded using MedDRA version 24.1. The number and percent of subjects reporting various medical, family and psychiatric histories, grouped by MedDRA system organ class (SOC) and preferred term (PT), will be tabulated by treatment group for the safety population. The denominator used for calculating the percentages will be the total number of

---

subjects included in the safety population in each treatment group. Retrospective 3-month headache history will be listed.

### **6.10.3. Protocol Deviations**

A protocol deviation is defined as any change, divergence, or departure from the study design or procedures defined in the protocol. An important protocol deviation (IPD) is defined as a protocol deviation that might significantly affect the completeness, accuracy, and/or reliability of the study data or that might significantly affect a subject's rights, safety, or well-being.

Potential IPDs may include, but are not limited to:

- Subjects who received the study medication but did not meet all the inclusion or met any of the exclusion criteria.
- Subjects who received non-randomized study medication.
- Subject's treatment compliance < 80% or > 120%.

Prior to the database lock and break of treatment blind, potential IPDs identified in the clinical database and/or recorded in the site deviation log will be reviewed by clinical monitor and study team for the determination of IPDs, which would lead to the exclusion from the PP Population. IPDs will be summarized and listed for the randomized population.

### **6.11. Exposure and Compliance**

Duration of exposure is defined as the total number of days a subject is exposed to study medication (SM). This will be calculated for each subject by taking the difference between the date of SM last dose minus the date of SM first dose, plus 1 (date of last dose minus date of first dose +1).

Treatment duration will be categorized in days as: completed Day 1 to  $\leq$  Day 28, completed Day 29 to  $\leq$  Day 56, completed Day 57 to  $\leq$  Day 84, completed Day 85 to  $\leq$  Day 112, completed Day 113 to  $\leq$  Day 141, and completed  $>$  Day 141. The number and percentage of subjects in each duration group will be summarized by treatment group for the Safety population.

Duration of treatment exposure will also be summarized using descriptive statistics (n, mean, SD, median, Q1, Q3, minimum, and maximum) for safety population.

Percent of study drug compliance is defined in Section 4.

[figure not shown]
[figure not shown]
For each treatment, SM compliance will be summarized by compliance category (<80%, 80-120%, and >120%) and number of subjects in each compliance category. Study medication compliance will also be summarized as a continuous variable using descriptive statistics (number and percent for each treatment).

[figure not shown]
Summaries of treatment compliance and exposure will be presented separately for the Titration Period, Maintenance Period and combined Titration and Maintenance Periods.

[figure not shown]
[figure not shown]
This analysis will be conducted for the Safety Population. Derivations of duration of treatment exposure and compliance are defined in Section 4. All study medication administration, exposure, and accountability data collected will be listed.

[figure not shown]
## 7. Efficacy Analysis

[figure not shown]
Based on FAS, the observed value and change from baseline as well as descriptive statistics as described in Section 6.2 will be presented for all efficacy endpoints by study visit and treatment group. Subject listing of the observed value and change from baseline will be listed for all efficacy endpoints. The mean profile of 28-day MMDs will be presented by treatment group and study visit.

## **9. Safety and Tolerability Analysis**

All safety analyses will be performed on the Safety population. No inferential statistical tests will be performed.

### **9.1. Adverse Events**

All adverse events (AEs) will be coded using the MedDRA Version 24.1.

A treatment-emergent adverse event (TEAE) is defined as an AE with a start date on or after the date of the first dose of study medication, or that worsened in severity following the first dose of study medication. All AEs in this study will be recorded after administration of study medication, therefore all will be considered treatment-emergent.

---

The Investigator is responsible for determining the relationship between the administration of SM and the occurrence of an AE as not suspected or as a suspected reaction to SM. Non-suspected AEs will be those that are determined as not related or unlikely related. Suspected AE are those that are determined as possibly related or definitely related.

Adverse event severity grades are reported as mild, moderate, or severe.

Summaries of incidence rates (frequencies and percentages) of individual TEAEs will be presented by SOC, PT, and treatment group. Such summaries will be displayed for all TEAEs, TEAEs by maximum severity, and TEAEs by relationship.

Each subject will be counted only once within each category level (SOC and PT). If a subject experiences more than 1 TEAE within each category level, the TEAE with the strongest relationship or the maximum severity, as appropriate, will be included in the summaries of relationship and severity. If a particular event is missing the severity and/or relationship, then the strongest possible severity or relationship will be assumed for analysis (severity = severe, relationship = definitely related).

Incidence will be presented by descending frequency of SOC and PT within SOC, and then alphabetically within PT where the incidence is the same; this is based on overall subjects then alphabetically in case of a tie.

In addition, number and percent of patients reporting common AEs ( $\geq 5\%$  in any treatment group) will be presented by PT.

Missing and partially missing AE start and/or stop dates and times will be imputed, for the purpose of statistical analysis, according to the specifications described in Section [6.7.2](#).

In the AE data listings, all AEs will be displayed.

A summary of incidence rates (frequencies and percentages) of TEAEs leading to withdrawal of study medication, by treatment group, SOC, and PT will be prepared for the Safety Population.

Adverse events of special interest (AESI) include the following.

- Metabolic acidosis
- Hyperammonemia
- Oligohydrosis and hyperthermia
- Clinically significant increase in alkaline phosphatase, creatinine, or eosinophils (specifically, for patients 6 to 11 years, these were noted to be abnormally increased more frequently with TPM than with placebo)
- Clinically significant decrease in total white count or neutrophils
- Visual changes: subjects presenting with blurry vision, ocular pain, and visual field defects subjects must be discontinued early and closely followed to ensure a prompt resolution of ocular AEs.
- Suicidal behavior and ideation

- Cognitive and memory function impairments
- Nephrolithiasis

AESI for AE data will be identified in the AE eCRF page and flagged in the AE dataset. AESI for non-AE data will be identified by Supernus drug safety team based on data listings provided by statistical programming.

The incidence of AESIs based on AE data will be summarized for each treatment group by MedDRA SOC and preferred term. Supporting subject listing of AESI be presented.

A data listing of AEs leading to withdrawal of study medication will also be provided, displaying details of the event(s) captured on the CRF.

Any deaths that occur during the study will be listed. Serious adverse events will be listed and tabulated by SOC and PT and presented by treatment.

## **9.2. Clinical Laboratory Evaluations**

Laboratory tests (chemistry, hematology, and urinalysis) will be performed at Screening, Prospective Baseline, and every visit of the Treatment Phase and Post-treatment (EOS/ET) Phase. Results will be summarized descriptively by treatment group and study visit as both observed values and change from baseline values. See Section 4 for the definition of baseline. Number and percentage of subjects with abnormal qualitative urinalysis results will be provided by treatment group and study visit.

Laboratory values for clinical chemistry and hematology will be presented by visit using descriptive statistics (n, mean, SD, median, Q1, Q3, minimum, and maximum) by treatment group for the actual and change from baseline values will be presented in Tables. If there are multiple values for a given visit, the worst value will be used for that visit.

Laboratory values for clinical chemistry and hematology will be flagged as abnormally low (L) if the value < lower limit of the normal range, normal (N) if the value is within normal range or abnormally high (H) if the value > upper limit of the normal range. In addition, shift tables for the change from baseline to all study visits and to the worst post-baseline will be presented.

Laboratory values will be displayed in the data listings and those that are outside the normal range will be flagged and presented along with corresponding normal ranges (if available). A separate listing of abnormal laboratory values will be provided. All study visits within a parameter for a subject will be presented if at least 1 study visit within that parameter has an abnormal result.

Urine pregnancy tests, urine drug screens and serum pregnancy test results will be listed separately.

## **9.3. Vital Signs**

Vital signs will be collected at all study visits. Descriptive summaries of actual values and changes from baseline will be calculated for weight (kg), BMI (kg/m^2), oral body temperature (°C), respiration rate (breaths per minute), sitting heart rate (bpm), sitting systolic blood pressure

(mmHg) and sitting diastolic blood pressure (mmHg). These summaries will be presented by study visit and treatment group. See Section 4 for the definition of baseline.

The number of subjects with vital signs values below, within, or above normal ranges, by study visit as well as to the worst post-baseline will be tabulated (shift tables) for each vital sign parameter by treatment group. Normal ranges are presented in the below table.

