- d. Physical examination (excluding genitourinary system) includes height and weight and a special assessment for the occurrence of decreased sweating and elevation in body temperature above normal. Neurological examination includes evaluation for impaired reflexes, balance problems, muscle weakness, paresthesia/numbness and tingling, speech difficulties, mental confusion or excessive fatigue.
- e. Seated (5 min) pulse rate, blood pressure, temperature, and respiratory rate. The vital signs' readings, except prior to dosing, will be performed within approximately 10 minutes prior to scheduled blood draws, where applicable.
- f. Concomitant medication includes headache rescue medicine (also recorded in the Headache Diary).
- g. Headache Diary training will be provided at Visit 2.

- h. Subjects will start the first dose on the same day of Visit 3 at the clinical site, instructions for dose titration will be provided.
- i. Provide instructions for dose tapering at Visit 8.
- j. Any subject who experiences an AE (whether serious or non-serious) or has a clinically significant abnormal laboratory test value will be followed by the Investigator for up to 30 days after the EOS visit. These subjects will be treated and/or followed up until the symptoms or value(s) return to normal/baseline or acceptable levels, as determined by the Investigator.

l. Safety Follow Up (by Phone) is not a site visit and falls within a range of 1-3 weeks after Visit 9/ET Visit occurs.

m. Subjects who discontinue from the study earlier than the EOS visit (visit 9) should undergo all EOS procedures included in visit 9 during the ET visit.

Note: Besides the testing specified during the respective visits in the Table 2 above, repeat testing for clinical laboratory parameters, vital signs, and/or ECG may be permitted, at the discretion of the Investigator. However, these repeat testing will require justification from the site and agreement with the Medical Monitor and the Sponsor on a case-by-case basis prior to conducting the tests.

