5.1.1 Visit 1 – Screening (Day -56)

All reasons for screening failure will be recorded. If the subject passes screening but fails eligibility at Randomization visit (Visit 3), the reason(s) will also be recorded in the eCRF.

For subjects eligible for study participation, a Prospective Baseline Visit will be scheduled allowing for at least a 2-week/14-day washout of any disallowed migraine preventative medications the subject was receiving at Screening.

The following assessments will be conducted at this visit (screening assessments may be performed over multiple days):

- Obtain written informed consent/assent
- Obtain demographics
- Collect retrospective headache history, including non-pharmacological adjunctive treatments (last 3 months)
- Review inclusion/exclusion criteria
- Collect medical, family and psychiatric histories
- Perform physical examination (excluding genitourinary system) including height, weight and neurological examination
- Perform visual neurological exam
- Perform 12-lead ECG
- Record vital signs (pulse rate, blood pressure [BP], temperature, and respiration rate [RR])
- Collect blood samples for hematology and serum chemistry
- Collect serum sample for pregnancy testing (FOCP only)
- Collect urine sample for drug screen and urinalysis
- Administer C-SSRS
- Administer PedMIDAS scale
- Record concomitant medications

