5.1.3 Visit 3 (+2 days) – Randomization (Day 1)

The following assessments will be conducted at this visit:

- Review inclusion/exclusion criteria
- Record vital signs (pulse rate, BP, temperature, and RR)
- Collect urine sample for pregnancy test (FOCP only)
- Administer C-SSRS
- Review and record concomitant medications
- Review Headache Diary for eligibility
- Administer PedMIDAS, PedsQL 4.0 scales
- Perform cognitive assessment
- Perform eye exam
- Record AEs
- Randomization
- Dispense SM (4-week supply) and provide instructions for dose titration

5.1.4 Titration Period (Days 1 to 56, Week 1 to end of Week 8)

Intervening Phone Calls

At Days 14 (± 2 days) and 43 (± 2 days) there will be telephone calls to subjects to assess the tolerability of the SM treatment.

The following assessments will be made during these telephone contacts:

- Review and record concomitant medications
- Record AEs
- Provide guidance (as needed) on dose reduction

Visit 4 (Day 29 \pm 7 days)

During Treatment Phase (Visits 4 through 9), sample collection and testing have been specified for respective visits by the Sponsor. Besides the testing specified during these respective visits, repeat testing for clinical laboratory parameters, vital signs, and/or ECG may be permitted, at the discretion of the Investigator. However, these repeat testing will require justification from the site and agreement with the Medical Monitor and the Sponsor on a case-by-case basis prior to conducting the tests.

The following assessments will be conducted at this visit:

- Perform physical examination (excluding genitourinary system) including height and weight, and neurological examination

- Record vital signs (pulse rate, BP, temperature, and RR)
- Collect urine sample for pregnancy test (FOCP only)
- Administer C-SSRS
- Review and record concomitant medications
- Review Headache Diary
- Record AEs
- Collect SM and assess adherence; retrain as needed
- Dispense SM (4-week supply) and review medication instructions with subject and caregiver
- Placebo training refresher

5.1.5 Maintenance Period (Days 57 to 140, Week 9 to the end of Week 20)

Visit 5 (Day 57 ± 7 days)

The following assessments will be conducted at this visit:

- Perform 12-lead ECG
- Record vital signs (pulse rate, BP, temperature, and RR)
- Collect blood samples for hematology and serum chemistry
- Collect urine sample for urinalysis and for pregnancy test (FOCP only)
- Collect urine sample for drug screen

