6.6.9 Adverse Events of Special Interest

An AESI (serious or non-serious) is one of scientific and medical concern specific to the sponsor's product or program, for which ongoing monitoring and rapid communication by the investigator to the sponsor can be appropriate. Such an event might warrant further investigation in order to characterize and understand it. Depending on the nature of the event, rapid communication by the trial sponsor to other parties (e.g., regulatory agencies, IRB, etc.) might also be warranted.

Several AEs are known to be associated with the long-term use of TPM and can be expected with treatment with SPN-538 (["National Institutes of Health-DailyMed- Trokendi XR- Prescribing Information.," 2022](#)). Consistent monitoring is required for the following AESIs:

- Metabolic acidosis (serum bicarbonate)
- Hyperammonemia
- Oligohydrosis and hyperthermia
- Clinically significant increase in alkaline phosphatase, creatinine, or eosinophils (specifically, for patients 6 to 11 years, these were noted to be abnormally increased more frequently with TPM than with placebo)
- Clinically significant decrease in total white cell count or neutrophils
- Visual changes: subjects presenting with blurry vision, ocular pain, and visual field defects must be discontinued early and closely followed to ensure a prompt resolution of ocular AEs.

- Suicidal behavior and ideation
- Serious skin reactions (TPM should be discontinued at the first sign of rash, unless rash is not drug-related)
- Negative effect on growth (weight and height)
- Cognitive and memory function impairments
- Nephrolithiasis

The Site Investigator must report all AESIs to Supernus drug safety team within 24 hours of becoming aware of the information using the SAE/AESI Report form.

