6.8.5 Physical and Neurological Examinations

The physical examination conducted at Screening will include assessments of all body systems other than genitourinary and at visits designated on the Schedule of Events and Assessments ([Table 2](#)). Measurement of height, and weight will be performed to monitor for signs of growth retardation. A special assessment will be made regarding the occurrence of decreased sweating and an elevation in body temperature above normal. Any findings during screening will be recorded as medical history, and any clinically significant abnormal findings during treatment will be recorded as an AE. At the EOS physical examination, only changes from baseline (Screening visit) will be noted.

Routine neurological exam at Screening will be aimed at detecting any possible causes of headache other than migraine. After the initiation of treatment, a neurological evaluation will help to assess for effects of SPN-538 on the nervous system, such as

impaired reflexes, balance problems, muscle weakness, paresthesia/numbness and tingling, speech difficulties, mental confusion or excessive fatigue. As part of the visual neurological examination, the following will be assessed at Visits 1 and 9: extraocular movements, pupils and confrontation visual fields for each eye ([Appendix 10.7](#)).

Equipment necessary for this part of the examination listed in the next section under Eye Exam.

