### **9.5.     Physical, Neurological and Eye Examination**

Physical examinations will include assessments of all body systems except genitourinary as well as height and weight and a special assessment for the occurrence of decreased sweating and elevation in body temperature above normal. Neurological examination will include evaluation for impaired reflexes, balance problems, muscle weakness, paresthesia/numbness and tingling, speech difficulties, mental confusion or excessive fatigue. Eye examinations will measure visual acuity and visualize the optic disc through a fundoscopic exam. Subjects will be monitored for visual/ocular disturbances and potential signs of angle closure glaucoma during the participation in the study

Any findings during screening will be recorded as medical history and any clinically significant abnormal findings during treatment will be recorded as an AE. At the EOS physical and neurological examinations, only changes from the screening visit will be noted.

All physical, neurological and eye examination results will be listed.

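### Height is measured at six visits to monitor growth, but no by-visit, by-arm summary of height or height change is planned

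*SAP*

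**What the plan says.** **Why height is measured.** The Protocol Introduction names negative effects on growth among the topiramate-attributable effects that need continuing assessment. Protocol 6.8.5 states the purpose: "Measurement of height, and weight will be performed to monitor for signs of growth retardation". The adverse events of special interest in Protocol 6.6.9 include the item beginning "Negative effect on growth (weight and height".

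**When it is measured.** At Screening (5.1.1) the instruction is "Perform physical examination (excluding genitourinary system) including height, weight and neurological examination". For Visits 4, 6, 7, 8 and 9 (5.1.4 to 5.1.6) it is "Perform physical examination (excluding genitourinary system) including height and weight, and neurological examination". The Table 2 footnote agrees: "Physical examination (excluding genitourinary system) includes height and weight and a special assessment".

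**How it is analysed.**
- SAP 9.3: "Descriptive summaries of actual values and changes from baseline will be calculated for weight (kg), BMI", followed by temperature, respiration rate, heart rate and the two blood pressures, by visit and treatment group. Height is not named, and it has no row in the normal-range table that follows.
- SAP 9.5 places height within the physical examination and ends: "All physical, neurological and eye examination results will be listed".
- SAP 6.10.2, on baseline characteristics: "height and weight at screening will be summarized for the ITT population".
- Protocol 7.11 plans, for the physical, neurological and eye examinations, a by-arm summary of change in status to end of study, arranged by body system.
- SAP 9 rules out inferential tests on safety data.

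**The concern.** Impaired growth is a risk the sponsor itself names for this drug, and the participants are children aged 6 to 11. The usual way to look for a modest effect on growth is to compare mean height change between the randomised arms. No single child need look abnormal for the arms to differ on average. The plan collects what is needed for that comparison and then specifies no summary of it. If the SAP is followed as written, the study report would show weight and BMI by visit and arm but no mean height after Screening. The report could then give no planned estimate, reassuring or otherwise, of the difference in height gain.

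**Working it through.** **1. Count the measurements.** The visit lists in Protocol 5.1.1 to 5.1.6 include height at Visit 1 (Day -56), Visit 4 (Day 29), Visit 6 (Day 85), Visit 7 (Day 113), Visit 8 (Day 141) and Visit 9 (Day 162). That is 6 in total, 5 of them after randomisation. Visits 2, 3 and 5 have no physical examination. The physical-examination row of Table 2 in the protocol gives the same six visits.

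**2. Look for a by-arm summary of post-Screening height.**
- SAP 9.3: by visit and arm, but height is not named.
- SAP 9.5: height is included, but as a listing.
- SAP 6.10.2: height is summarised, but only at Screening.
- SAP 9.1: adverse events by arm, which captures height only if an event is reported. As printed, the special-interest list there does not include growth.
- Protocol 7.11: by arm, but a categorical status by body system, not a measurement.
- Protocol synopsis, safety analyses: weight is named, height is not.

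Planned by-arm summaries of measured height or height change after Screening: 0. SAP 9.3 and 9.5 show no blacked-out text at these points.

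**3. Can weight and BMI stand in?** BMI = weight / height². Take an illustrative child of 30 kg (assumed):
- At 130 cm: 30 / 1.30² = 17.75 kg/m².
- At 129 cm: 30 / 1.29² = 18.03 kg/m².

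A 1 cm shortfall at equal weight therefore raises BMI by (130/129)² − 1 = 1.6%. The rise is 1.7% at 120 cm and 1.4% at 140 cm. In this example the child crosses the SAP's lower normal limit of 18 kg/m², so the shift table would show a move from below normal to normal. If the shorter child also weighs 17.75 × 1.29² = 29.54 kg, which is 0.46 kg less, BMI does not change at all. Weight is tabulated beside BMI, so the pair carries some information about height. But BMI is a ratio formed within each child, so mean height cannot be recovered from mean weight and mean BMI.

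**4. What would an added row deliver?** The documents give no figure for height, so the sample size is the only input to reproduce. With difference 1.1, SD 3, 80% power and two-sided 5%:

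n per arm = 2 × (1.960 + 0.842)² × 3² / 1.1² = 116.8, so 117.

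Total randomised = 234 / 0.85 = 275.3, so 276, or 138 per arm. Both match Protocol 7.9.

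The 95% half-width for a difference in mean height change is 1.96 × SD × √(2/n). The SDs are assumptions.

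| SD of change (cm) | n = 117 per arm | n = 138 per arm |
|---|---|---|
| 1.0 | 0.26 cm | 0.24 cm |
| 1.5 | 0.38 cm | 0.35 cm |
| 2.0 | 0.51 cm | 0.47 cm |

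The 117 is the planned number of completers, a reasonable guide to the number with a Visit 8 height. The Safety Analysis Set can be larger, up to the 138 randomised.

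**5. Which baseline?** The SAP's general rule is the last value before first dose. With no height scheduled at Visits 2 or 3, that is Screening, up to 8 weeks earlier. A change to Visit 8 then spans up to 8 + 20 = 28 weeks, of which up to 8/28 = 29% is before treatment.

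**The case against.** The strongest reply is that the gap is narrow and that other parts of the plan would show a growth problem.

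- **Other by-arm summaries exist.** Protocol 7.11 still plans a change-in-status summary of examinations by arm, and SAP 10 says the planned analyses are unchanged. Clinically significant examination findings during treatment are recorded as adverse events and tabulated by arm. Growth is reportable as an event of special interest, and SAP 9.1 has the sponsor's safety team identify such events from listings of non-AE data. This stands. A reader might infer that growth is never compared between arms, or that a difference could be found only by reading listings. The documents do not support that: a recognised growth problem would reach by-arm tables. These routes depend on a problem being noticed in an individual child, however, and none yields a mean height change.
- **Weight sits beside BMI.** Flat weight with rising BMI would hint at reduced height gain. This stands as a hint, so it would be too strong to say that the two tables are blind to height. They still do not give mean height.
- **No named endpoint is left out.** Physical examinations are a safety endpoint, but height by itself is not, and SAP 9.3 does not say that its list is exclusive. Both points are fair and keep the grade down. Height is nevertheless on no summary list after Screening.
- **The remedy has limits.** The Screening baseline takes in untreated growth, and raw centimetres pool ages 6 to 11 and both sexes. Randomisation makes both features comparable between arms in expectation. They add noise rather than a systematic difference, and the table should say so.
- **No loss is demonstrated.** The documents give no expected height effect over 20 weeks and no SD. This is correct: the half-widths describe what the table could show, not an effect that would be missed.

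**Conclusion.** The point holds as an omission from the descriptive safety analysis. Height is measured six times, five after randomisation, for a stated growth-monitoring purpose, and no by-visit, by-arm summary of height or height change is planned. A modest mean difference in height gain would not appear in any planned table, although growth problems reported as adverse events would.

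The change should be made, but it is not critical. It does not touch the primary efficacy conclusion, the heights are collected and listed, and a comparison could still be produced after the fact. The case for acting now is that the SAP exists to fix analyses before database lock, and this is a named risk in a pediatric study. The precision of about ±0.26 to ±0.51 cm with 117 per arm rests on assumed SDs of 1.0 to 2.0 cm. The BMI example rests on an assumed 30 kg child of 129 or 130 cm.

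**What to change.** In SAP 9.3, add height (cm) to the parameters summarised by visit and treatment group, as actual value and change from the Screening value. Show the Visit 8 between-arm difference in mean change with a 95% confidence interval, on the Safety Analysis Set. Present it descriptively with no test, in keeping with SAP 9. Add a note that the height baseline is Screening, up to 8 weeks before first dose, so the change includes some untreated growth in both arms.

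The cost is one more parameter in an existing table, one interval and one footnote. No extra visit, measurement or data field is needed.
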